#### *Pharmacokinetics:*

Trough concentrations (or minimum concentrations [Cmin]) were collected in two Phase 3 studies (REGARD and RAINBOW) in patients with gastric cancer. Following the recommended clinical dose regimen, 8 mg/kg every 2 weeks, observed Cmin values were similar between

REGARD and RAINBOW, as noted in the table below (Investigator's Brochure, [Table 6.1](#)). The geometric mean observed trough values were approximately 50 ug/mL and approximately 60 to 70 ug/mL before the fourth and seventh doses, respectively.

**Table 6.1. Summary of Observed Ramucirumab Trough Concentrations for Patients with Advanced Gastric Cancer Following Administration of 8 mg/kg of Ramucirumab Every 2 Weeks as an IV Infusion over Approximately 1 Hour Alone (REGARD) or in Combination with Paclitaxel (RAINBOW)**

Dose Number	Trough a Serum Concentrations (ug/mL)			
	4		7	
	REGARD	RAINBOW	REGARD	RAINBOW
n PK	53	203	34	142
Geo Mean	49.5	45.0	74.4	62.8
Geo CV%	81	50	58	47

Abbreviations: CV% = percentage coefficient of variation; Geo = geometric; IV = intravenous; nPK = number of pharmacokinetic observations included in calculation.

a Trough concentrations were obtained prior to Doses 4 and 7. They also represent Cmin following Doses 3 and 6.

Pharmacokinetic data were from pooled from 8 studies including 497 patients with various malignancies for a population pharmacokinetic (PopPK) analysis. In these studies, ramucirumab was administered as a 1-hour I.V. infusion, at either 8 mg/kg once every 2 weeks on a 14- or 28-day cycle, or 10 mg/kg every 3 weeks on a 21-day cycle. The geometric mean (percentage coefficient of variation [CV%]) of PopPK model-derived estimates of ramucirumab clearance (CL), volume of distribution at steady state (Vss) and terminal half-life (t1/2) were 0.0140 L/h (29.8%), 5.5 L (14.4%), and 15 days (24.1%), respectively. These parameter estimates were consistent with those observed with other human monoclonal IgG1 (Keizer et al. 2010) antibodies. Results from the PopPK analyses indicate that the PK of ramucirumab following 8- and 10-mg/kg dose administrations were dose linear (absolute dose range: 169 to 1234 mg) and time independent.

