3.1.9 The effects of ramucirumab on the developing human fetus are unknown. For this reason and because anti-angiogenic agents are known to be teratogenic, women of child-bearing potential and men must agree to use adequate contraception (hormonal or barrier method of birth control; abstinence) prior to study entry and for the duration of study participation. Should a woman become pregnant or suspect she is pregnant while she or her partner is participating in this study, she should inform her treating physician immediately. Men treated or enrolled on this protocol must also agree to use adequate contraception prior to the study, for the duration of study participation, and 4 months after completion of ramucirumab administration.

3.1.10 Ability to understand and the willingness to sign a written informed consent document.

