### 5.5 **Criteria for Taking a Participant Off Protocol Therapy**

Duration of therapy will depend on individual response, evidence of disease progression and tolerance. In the absence of treatment delays due to adverse event(s), treatment may continue until one of the following criteria applies:

- Disease progression
- Intercurrent illness that prevents further administration of treatment
- Unacceptable adverse event(s) or adverse event(s) requiring discontinuation of therapy as specified in the dose modification section of this protocol
- Participant demonstrates an inability or unwillingness to comply with the treatment regimen and/or documentation requirements
- Participant decides to withdraw from the protocol therapy
- General or specific changes in the participant's condition render the participant unacceptable for further treatment in the judgment of the treating investigator

Participants will be removed from the protocol therapy when any of these criteria apply. The reason for removal from protocol therapy, and the date the participant was removed, must be documented in the case report form (CRF). Alternative care options will be discussed with the participant.

For Centralized Subject Registrations, the research team submits a completed Off Treatment/Off Study form to ODQ when a participant comes off study. This form can be found on the ODQ website or obtained from the ODQ registration staff.

For Decentralized Subject Registrations, the research team updates the relevant Off Treatment/Off Study information in OnCore.

In the event of unusual or life-threatening complications, treating investigators must immediately notify the Overall PI, [name] at [contact].

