### 5.6 **Duration of Follow Up**

Subject survival and subsequent therapy information will be collected, preferably via office visit or telephone contact, every 6 months +/- 1 week from the date of last dose of study drug until the subject's death or until the subject is lost to follow-up, or until study closure. For patients who discontinue therapy prior to disease progression, a physical exam, performance status, Chromogranin A, and radiographic imaging will be assessed every 12 weeks +/- 1 week until tumor progression or start of new anticancer therapy.

Participants removed from protocol therapy for unacceptable adverse event(s) will be followed until resolution or stabilization of the adverse event.

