### **5.7 Criteria for Taking a Participant Off Study**

Participants will be removed from study when any of the following criteria apply:

- Lost to follow-up
- Withdrawal of consent for data submission
- Death

The reason for taking a participant off study, and the date the participant was removed, must be documented in the case report form (CRF).

For Centralized Subject Registrations, the research team submits a completed Off Treatment/Off Study form to ODQ when a participant comes off study. This form can be found on the ODQ website or obtained from the ODQ registration staff.

For Decentralized Subject Registrations, the research team updates the relevant Off Treatment/Off Study information in OnCore.

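### Criterion 3.1.9 gives men a contraception minimum of 4 months after the last ramucirumab dose but gives women of child-bearing potential no dose-linked minimum

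*Combined protocol and SAP*

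**What the plan says.** Criterion 3.1.9 (Section 3.1) gives class teratogenicity as the reason for contraception and asks women of child-bearing potential, and men, to use it "prior to study entry and for the duration of study participation". A later sentence, for men only, sets the period as "for the duration of study participation, and 4 months after completion of ramucirumab administration". The sentence between them asks a woman to report a pregnancy, or a suspected one, that occurs "while she or her partner is participating in this study", so it too has no dose-linked end.

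The protocol does not define participation. Three sections bear on it:

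- Section 5.5 covers leaving treatment. One of its reasons is "Participant decides to withdraw from the protocol therapy".
- Section 5.6 continues survival contact every 6 months from the last dose until death, "or until the subject is lost to follow-up, or until study closure".
- Section 5.7 takes a patient off study for loss to follow-up, death, or "Withdrawal of consent for data submission".

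None of the three mentions contraception. Criterion 3.2.18 excludes pregnant and breastfeeding women at entry, and the study calendar (Section 9) marks the pregnancy test at pre-study only. No other section of the available text gives women an interval after the last dose.

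**The concern.** The fixed post-dose minimum goes only to the sex in whom fetal exposure would be indirect. A man who leaves shortly after an infusion has already agreed to 4 months. A woman who leaves at the same point has agreed to no post-dose interval, although any fetal exposure in her would be direct. Section 2.2.1 adds that no animal studies have specifically addressed female reproduction or fetal development.

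A protocol cannot enforce contraception once someone has left. The agreement made at entry, and the advice given with it, are therefore the safeguard. The stake is patient safety; the efficacy analysis is not involved.

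**Working it through.** This is mainly a comparison of texts. The plan gives no figure on the point to reproduce.

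**Step 1. What each reading of participation gives.**

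| Situation | Man | Woman |
|---|---|---|
| Participation ends off study (5.7); patient stays in follow-up | Follow-up period, and at least 4 months after last dose | Follow-up period, plausibly beyond 4 months |
| Same reading; patient withdraws consent or is lost soon after a dose | 4 months after last dose | No post-dose minimum |
| Participation ends with treatment (5.5) | 4 months after last dose | No post-dose minimum |

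The separation of 5.5 from 5.7 favours the first reading. The men's sentence points the other way: if participation normally ran to death or study closure, the added 4 months would be redundant for most men. The text does not settle it.

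**Step 2. Whether drug is still present in that window.** All inputs are from the pharmacokinetics text in Section 2.2.1, at the regimen used here (8 mg/kg every 14 days, Section 5.1).

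- Clearance, volume at steady state and terminal half-life: "0.0140 L/h (29.8%), 5.5 L (14.4%), and 15 days (24.1%), respectively".
- Observed geometric mean troughs before dose 7, that is 14 days after dose 6: 62.8 ug/mL (RAINBOW) and 74.4 ug/mL (REGARD). These are gastric cancer patients, used as a guide.

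The half-life implied by clearance and volume is ln 2 × 5.5 / 0.0140 = 272.3 h = 11.35 days. The stated terminal value is 15 days. Assuming first-order decline, the share of the last-dose level remaining is 0.5^(days / half-life):

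| Days after last dose | Half-life 11.35 d | Half-life 15 d |
|---|---|---|
| 14 | 42.5% | 52.4% |
| 30 | 16.0% | 25.0% |
| 75 | 1.0% | 3.1% |
| 122 (about 4 months) | 0.06% | 0.36% |

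Treating the half-life as log-normal, one log-SD above 15 days (CV 24.1%, log-SD 0.238) is 19.0 days, which leaves 1.2% at 122 days.

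**Step 3. Projection from the observed troughs.**

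- Day 30 (16 days after the trough): 62.8 × 0.5^(16/11.35) = 23.6 ug/mL to 74.4 × 0.5^(16/15) = 35.5 ug/mL.
- Day 122 (108 days after the trough): 62.8 × 0.5^(108/11.35) = 0.09 ug/mL to 74.4 × 0.5^(108/15) = 0.51 ug/mL.

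The terminal half-life overstates early levels, so the 15-day column is an upper end. The late values are probably high as well. Section 2.2.1 attributes linear kinetics at and above 8 mg/kg to saturation of target-mediated clearance, and that saturation would be expected to lift as levels fall.

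**The case against.** The strongest reply is that 5.7 defines when a patient leaves the study and 5.5 governs treatment only. A woman who merely stops treatment then stays on study and remains covered, often for longer than 4 months. Loss to follow-up also tends to be found late. The first survival contact falls about 6 months after the last dose, already past 122 days. For patients who stop before progression, a 12-week visit (±1 week), if counted from the last dose, falls at 77 to 91 days, when 2.9% to 1.5% remains at a 15-day half-life. On this view the clearest remaining case is withdrawal of consent shortly after a dose. The consent pages and the Investigator's Brochure were also not available, and either may give women an interval. Finally, nothing in the documents links a drug level to fetal harm, and entry exclusions and a baseline pregnancy test are in place.

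Much of this stands and narrows the reach of the point. It does not close the gap. Participation is nowhere expressly tied to 5.7. A woman who withdraws consent has no minimum on either reading, and the protocol does not say when loss is declared, so a woman on treatment could be classed as lost early. The entry safeguards do not act after a dose. If the Brochure does state an interval, that is a reason to bring 3.1.9 into line with it.

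**Conclusion.** The concern holds as a finding about the wording of 3.1.9, not about what women were actually told. Under the broad reading the gap is narrow: women who withdraw consent or are lost soon after a dose. Under the narrow reading it covers every woman of child-bearing potential. In the first month after a dose a material share of drug remains (16-25% at 30 days), while by 4 months under 0.4% does, or about 1.2% at the longer 19-day half-life. The period asked of men would therefore cover nearly all of the washout in women too.

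This rests on first-order decline and on carrying over pharmacokinetics from other, mainly gastric, cancers. How many of the 43 patients would be affected cannot be estimated from the documents and may be few. The change is still worth making, because the possible harm is serious and the correction is small.

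**What to change.** Amend 3.1.9 so that women of child-bearing potential agree to contraception during treatment and for a stated interval after the last ramucirumab dose, whatever their study status. Take the interval from the Investigator's Brochure. If it gives none, use at least the 4 months already asked of men. The documents give no rationale for 4 months, so it serves only as a default for consistency. Apply the same window to the pregnancy-notification sentence, and check that the participant information agrees.

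The cost is one sentence in 3.1.9 and the matching notification wording, plus participant information if it differs. Some women would take on a more explicit and possibly longer commitment. Sample size, power and analysis are unaffected.

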## **3.2 Exclusion Criteria**

- 3.2.1 Patients who have had chemotherapy or radiotherapy within 4 weeks prior to entering the study or those who have not recovered from adverse events due to agents administered more than 4 weeks earlier.
- 3.2.2 Patients who have undergone major surgery within 28 days or subcutaneous venous access device placement within 7 days prior to study enrollment.
- 3.2.3 Patients with elective or planned major surgery to be performed during the course of the clinical trial.
- 3.2.4 Patients who are receiving any other investigational agents.
- 3.2.5 Patients with any Grade 3-4 gastrointestinal bleeding within 3 months prior to enrollment.
- 3.2.6 Patients with a history of deep vein thrombosis, pulmonary embolism, or any other significant thromboembolism (venous port or catheter thrombosis or superficial venous thrombosis are not considered “significant”) during the 3 months prior to registration.
- 3.2.7 Patients who have experienced any arterial thromboembolic events, including but not limited to myocardial infarction, transient ischemic attack, cerebrovascular accident, or unstable angina, within 6 months prior to enrollment.
- 3.2.8 Patients with uncontrolled or poorly-controlled hypertension (>160 mmHg systolic or > 100 mmHg diastolic for >4 weeks) despite standard medical management.
- 3.2.9 Patients who have congestive heart failure (NYHA Class III or IV), sustained ventricular tachycardia, ventricular fibrillation, clinically significant bradycardia, advanced heart block within the six months preceding enrollment.

- 3.2.10 Patients who have cirrhosis at a level of Child-Pugh B (or worse) or cirrhosis (any degree) and a history of hepatic encephalopathy or clinically meaningful ascites resulting from cirrhosis.
- 3.2.11 Patients with a serious or nonhealing wound, ulcer, or bone fracture within 28 days prior to enrollment.
- 3.2.12 Patients receiving chronic antiplatelet therapy, including aspirin, nonsteroidal anti-inflammatory drugs (NSAIDs, including ibuprofen, naproxen, and others), dipyridamole or clopidogrel, or similar agents. Once-daily aspirin use (maximum dose 325 mg/day) is permitted.
- 3.2.13 Patients with uncontrolled brain or leptomeningeal metastases, including patients who continue to require glucocorticoids for brain or leptomeningeal metastases.
- 3.2.14 Patients with prior or concurrent malignancy except for the following: adequately treated basal cell or squamous cell skin cancer, or other adequately treated *in situ* cancer, or any other cancer from which the patient has been disease free for five years.
- 3.2.15 Patients with symptomatic cholelithiasis.
- 3.2.16 Patients who have any severe and/or uncontrolled medical conditions or other conditions that could affect their participation in the study such as:
  - Severely impaired lung function
  - Any active (acute or chronic) or uncontrolled infection/ disorders.
  - Nonmalignant medical illnesses that are uncontrolled or whose control may be jeopardized by the treatment with the study therapy
  - Psychiatric illness/social situations that would limit compliance with study requirement
- 3.2.17 History of allergic reactions attributed to compounds of similar chemical or biologic composition to ramucirumab .
- 3.2.18 Pregnant and breastfeeding women are excluded from this study because ramucirumab is associated with the potential for teratogenic or abortifacient effects. Because there is an unknown but potential risk for adverse events in nursing infants secondary to treatment of the mother with ramucirumab, breastfeeding should be discontinued if the mother is treated with ramucirumab. These potential risks may also apply to other agents used in this study.

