Ramucirumab demonstrated significant and clinically meaningful benefit in overall survival (OS) as a single agent at a dose of 8 mg/kg every 14 days in patients with advanced gastric cancer in the REGARD study, a randomized Phase 3 trial of ramucirumab monotherapy with best supportive care [BSC] versus placebo with best supportive care.(Fuchs, Tomasek et al. 2014) Ramucirumab also has shown clinical efficacy in patients with gastric cancer in combination with paclitaxel in a phase III study of paclitaxel with ramucirumab compared with paclitaxel with placebo (RAINBOW).(Wilke, Muro et al. 2014) A Phase 3 trial (ROSE) examining the combination of ramucirumab with docetaxel in previously untreated metastatic breast cancer failed to meet its primary endpoint of investigator-assessed progression-free survival (PFS). In ROSE, while investigator-assessed PFS numerically favored ramucirumab, this difference was not statistically significant.(Mackey, Ramos-Vazquez et al. 2015)

Please refer to the current version of the Investigator's Brochure for updated information regarding the clinical experience and activity of ramucirumab.

*Adverse Events:*

As of 31 December 2013, AE information was available for 2485 patients receiving ramucirumab drug product (DP) on 7 Phase 1/1b studies, 18 open-label or unblinded Phase 2 studies, and 3 completed Phase 3 studies, including monotherapy and combination therapy with cytotoxic chemotherapy agents. Placebo-controlled blinded clinical trials are ongoing (1 Phase 2 study, 3 Phase 3 studies); unblinded safety data for these studies are not available. Detailed AE information based on a review of Phase 1/1b, Phase 2, and completed Phase 3 clinical studies of ramucirumab DP (N=2485) are available in the Investigator Brochure.

Adverse drug reactions (ADRs; AEs for which a causal relationship to the investigational drug was considered at least possible) of special interest include AEs which have been associated with antiangiogenic agents and therapeutic monoclonal antibodies and include the following categories: infusion-related reaction (IRR), hypertension, proteinuria, arterial thromboembolic events (ATEs), venous thromboembolic events (VTEs), bleeding/hemorrhagic events, gastrointestinal (GI) perforation, and congestive heart failure (CHF) when used in combination with mitoxantrone or following prior anthracycline therapy.

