## **3. PARTICIPANT SELECTION**

### **3.1 Eligibility Criteria**

3.1.1 Participants must have histologically or cytologically confirmed low- to intermediate-grade neuroendocrine tumor (carcinoid tumor).

- 3.1.2 Carcinoid tumors of any site are eligible. Patients with pancreatic neuroendocrine tumors are excluded.
- 3.1.3 Participants must have measurable disease, defined as at least one lesion that can be accurately measured in at least one dimension (longest diameter to be recorded for non-nodal lesions and short axis for nodal lesions) as  $\geq 20$  mm with conventional techniques or as  $\geq 10$  mm with spiral CT scan, MRI, or calipers by clinical exam. See Section 10 for the evaluation of measurable disease.
- 3.1.4 Locally advanced, unresectable or metastatic disease.
- 3.1.5 Patients must have evidence of radiographic disease progression within the past 12 months. Progressive disease by RECIST criteria is not required.
- 3.1.6 Age  $\geq 18$  years.
- 3.1.7 ECOG performance status 0-1 (see Appendix A).
- 3.1.8 Participants must have normal organ and marrow function as defined below:
- |                             |  |
|-----------------------------|--|
| - absolute neutrophil count | $\geq 1,000/\text{mm}^3$   |
| - platelets                 | $\geq 100,000/\text{mm}^3$   |
| - hemoglobin                | $\geq 9\text{ g/dL}$   |
| - total bilirubin           | $\leq 1.5 \times$ institutional upper limit of normal  |
| - AST(SGOT)/ALT(SGPT)       | $\leq 3 \times$ institutional upper limit of normal, or $\leq 5 \times$ institutional upper limit of normal in the setting of liver metastases   |
| - creatinine                | $\leq 1.5 \times$ upper limit of normal  |
| - urinary protein           | $\leq 1+$ on dipstick or routine urinalysis (if urine dipstick or routine urinalysis is 2+, a 24-hour urine collection for protein must demonstrate $<1000$ mg of protein in 24 hours)   |
| - coagulation function      | Adequate coagulation function as defined by International Normalized Ratio (INR) $\leq 1.5$ and a partial thromboplastin time (PTT) $< 1.5 \times$ institutional upper limit of normal. Patients on full-dose anticoagulation must be on a stable dose (minimum duration 14 days) of oral anticoagulant or low molecular weight heparin. |

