#### **6.3.7 Bleeding (Hemorrhagic) Events**

For Grade 3 or 4 bleeding (hemorrhagic) event bleeding: Discontinue ramucirumab.

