#### **6.3.8 Gastrointestinal Perforations or Fistula**

Ramucirumab should be discontinued in the event of a GI perforation or fistula formation.

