### 7.1 Expected Toxicities

#### 7.1.1 Adverse Event List(s) for ramucirumab

Please refer to the Investigator's Brochure for up to date information regarding adverse events associated with ramucirumab.

The most frequently observed, possibly related treatment-emergent adverse events (TEAEs) associated with ramucirumab include adverse events (AEs) which have been associated with antiangiogenic agents and therapeutic mAbs, and include the following categories: infusion-related reactions, hypertension, proteinuria, arterial thromboembolic events (ATEs), venous thromboembolic events (VTEs), bleeding/hemorrhagic events, gastrointestinal (GI) perforation, impaired wound healing, reversible posterior leukoencephalopathy syndrome (RPLS), and congestive heart failure (CHF) in patients who received ramucirumab following prior anthracycline therapy.

Table 7.2 of the Investigator's Brochure, summarized below, provides the frequency and severity of adverse drug reactions (ADRs) reported in  $\geq 5\%$  of ramucirumab-treated patients in the REGARD study, a single-agent, placebo-controlled Phase 3 gastric cancer study. The list below presents the frequency category of ADRs reported in the pooled safety analysis. ADRs are listed according to MedDRA system organ class. Within each system organ class, the adverse reactions are ranked by frequency, with the most frequent reactions first. In addition, the corresponding frequency category using the following convention (CIOMS III) is also provided for each

adverse reaction: very common ( $\geq 1/10$ ); common ( $\geq 1/100$  to  $< 1/10$ ); uncommon ( $\geq 1/1,000$  to  $< 1/100$ ); rare ( $\geq 1/10,000$  to  $< 1/1,000$ ); very rare ( $< 1/10,000$ )

Gastrointestinal Disorders Very common: abdominal pain, diarrhea	Nervous System Disorders Common: headache
Metabolism and Nutrition Disorders Common: hypokalemia, hyponatremia	Vascular Disorders Very common: hypertension

Clinically relevant ADRs reported in  $\geq 1\%$  and  $< 5\%$  of ramucirumab-treated patients in REGARD were: neutropenia, ATEs, intestinal obstruction, epistaxis, and rash. Clinically relevant reactions (including Grade  $\geq 3$ ) associated with antiangiogenic therapy observed in ramucirumab-treated patients across clinical trials were proteinuria, infusion-related reactions, and GI perforations.

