Table 7.3 of the Investigator's Brochure, summarized below, provides the frequency and severity of ADRs reported in  $\geq 5\%$  of ramucirumab-treated patients in the RAINBOW study, a phase III study of paclitaxel in combination with ramucirumab compared with paclitaxel with placebo in patients with advanced gastric cancer.

Blood and Lymphatic System Disorders Very common: leukopenia, neutropenia, thrombocytopenia	Renal and Urinary Disorders Very common: proteinuria
Gastrointestinal Disorders Very common: diarrhea, gastrointestinal hemorrhage, stomatitis	Respiratory, Thoracic, Mediastinal Disorders Very common: epistaxis
General Disorders Very common: fatigue, peripheral edema	Vascular Disorder Very common: hypertension
Metabolism and Nutrition Disorders Very common: hypoalbuminemia	

Clinically relevant ADRs reported in  $\geq 1\%$  and  $< 5\%$  of the ramucirumab plus paclitaxel treated patients in RAINBOW were GI perforations (1.2% for ramucirumab plus paclitaxel versus 0.3% for placebo plus paclitaxel) and sepsis (3.1% for ramucirumab plus paclitaxel versus 1.8% for placebo plus paclitaxel).

The most frequent ( $\geq 5\%$ ) ADRs observed in the open-label Phase 2 Study I4T-IE-JVBL (IMCL CP12-0917) for the nonsquamous population receiving ramucirumab plus platinum-based chemotherapy (pemetrexed plus carboplatin or cisplatin) are listed below.

Blood and Lymphatic System Disorders Very Common: anemia, neutropenia Common: thrombocytopenia, leukopenia	Nervous System Disorders Very Common: headache Common: dysgeusia, neuropathy
Gastrointestinal Disorders Very Common: nausea, vomiting Common: constipation, diarrhea, stomatitis	Respiratory, Thoracic Disorders Very Common: epistaxis Common: dyspnea

General Disorders Very Common: fatigued Common: peripheral edema	Skin and Subcutaneous Tissue Disorders Common: rash
Investigations Common: weight decrease	Vascular Disorders Very Common: hypertension
Metabolism and Nutrition Disorders Very Common: decreased appetite Common: hypomagnesemia	

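### Exclusion 3.2.5 covers recent Grade 3-4 bleeding only from the gastrointestinal tract, so a recent, resolved severe bleed elsewhere meets no specific bar to entry

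*Combined protocol and SAP*

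**What the plan says.** Section 3.2.5 excludes "Patients with any Grade 3-4 gastrointestinal bleeding within 3 months prior to enrollment". No other item in 3.1 or 3.2 names bleeding.

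Four other parts of the protocol bear on the scope of that rule:

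- **Tumor site.** Section 3.1.2 states: "Carcinoid tumors of any site are eligible". Pancreatic neuroendocrine tumors are the only exception.
- **Drug risk.** The adverse-event text in 2.2.1 lists, among the reactions of special interest, "bleeding/hemorrhagic events, gastrointestinal (GI) perforation, and congestive heart failure (CHF"; the bleeding category carries no site. Section 7.1.1 repeats it without a site. It also names a non-gastrointestinal bleed: for single-agent ramucirumab (REGARD), the reactions seen in at least 1% and under 5% of patients are "neutropenia, ATEs, intestinal obstruction, epistaxis, and rash". With paclitaxel (RAINBOW), the respiratory entry is "Very common: epistaxis".
- **Stopping rule.** Section 6.3.7 reads: "For Grade 3 or 4 bleeding (hemorrhagic) event bleeding: Discontinue ramucirumab". No site is given.
- **Laboratory limits.** Section 3.1.8 opens: "Participants must have normal organ and marrow function as defined below". The limits include hemoglobin of at least 9 g/dL, platelets of at least 100,000/mm³, INR of at most 1.5 and PTT below 1.5 times the upper limit of normal.

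**The concern.** The protocol already accepts that a severe bleed in the last 3 months is a reason not to start this drug. It then confines that reason to one organ system and does not say why. The population is not so confined, and neither are the drug's listed bleeding risk and the rule that stops it.

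What is at stake is patient safety. For a recent severe bleed outside the gastrointestinal tract, whether the patient receives a VEGFR-2 antibody depends on how the investigator reads a general clause. A named criterion would put a direct question on the eligibility checklist that 4.1 requires for each participant.

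**Working it through.** The main check is textual. Take a test patient: a Grade 3 airway or urinary bleed six weeks (42 days) before enrollment, now resolved, treated without major surgery, with all 3.1.8 values within limits.

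**Step 1. Apply each criterion that could catch this patient.**

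- 3.2.5: does not apply, because the bleed is not gastrointestinal. It is within the 3-month window and of the stated grade, so site is the only reason it escapes.
- 3.1.8: met by assumption. These are current laboratory values and do not ask about a past bleed.
- 3.2.2: major surgery within 28 days. Does not apply here; even a surgically treated bleed would be outside the window at 42 days.
- 3.2.7: includes cerebrovascular accident within 6 months. It could catch an intracranial bleed if read that way, although the item is framed as arterial thromboembolism. It does not reach the airway or urinary tract.
- 3.2.8 (uncontrolled hypertension), 3.2.12 (chronic antiplatelet drugs and NSAIDs) and 3.2.13 (uncontrolled brain or leptomeningeal metastases): each lowers bleeding risk indirectly. None asks about a past bleed.
- 3.2.16: a general clause on severe or uncontrolled conditions, or others that could affect participation. It can be invoked by judgement. Its listed examples do not mention bleeding.

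Result: no specific criterion bars the patient; one general clause may.

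**Step 2. Compare with how the protocol treats severe bleeding after entry.** Section 6.3.7 stops the drug for Grade 3-4 bleeding at any site. Section 6.3.5 allows treatment to resume during full-dose anticoagulation only if there has been no Grade 3 or 4 hemorrhage on study, again at any site. The second rule covers a single setting and on-study events only, but it is the same kind of decision as 3.2.5: a past severe bleed counts against further dosing.

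**Step 3. Price the change.** Section 12.2 gives 43 patients, 6 per quarter and 2 years of accrual. The documents give no frequency of recent severe non-gastrointestinal bleeding, so 0 to 2 patients needing replacement is an assumption.

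- Rate: 6 / 3 = 2 patients per month.
- No replacement: 43 / 2 = 21.5 months.
- One replaced (1/43 = 2.3%): 44 / 2 = 22.0 months, or +0.5.
- Two replaced (2/43 = 4.7%): 45 / 2 = 22.5 months, or +1.0.
- Planned capacity: 24 × 2 = 48 patients. Margin with two replaced: 24 − 22.5 = 1.5 months, before any pause for the safety review of the first 10 patients (5.1), whose length is not stated.
- The plan absorbs up to 48 − 43 = 5 replacements before 24 months is reached, again without a pause. The affordability of the fix therefore does not hinge on the upper limit of 2.

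**The case against.** The strongest reply is that the rule is a reasonable choice with adequate backing. Gastrointestinal hemorrhage is itself listed as very common in the RAINBOW table in 7.1.1, which makes a gastrointestinal bar understandable. Few criteria in 3.2 state a rationale, so a missing reason is not peculiar to 3.2.5. Section 3.2.16 is a binding exclusion, and an investigator confirms eligibility (4.1). Sites outside DF/HCC are not planned (4.3, 4.4), toxicity is examined after the first 10 patients, and the DSMC reviews it. Section 6.3.5 also leaves one tumor-bleeding decision to the treating physician.

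Most of this stands, and it limits the size of the point. It does not remove it. The authors had 3.2.16 available and still wrote 3.2.5, so they did not rely on the general clause for severe gastrointestinal bleeding. The early review, the DSMC and the stopping rule act only after a patient has been dosed.

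Three stronger readings are tempting and are not supported:

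- *That the entry and stopping rules contradict each other.* They need not mirror one another, and nothing in the documents says they should.
- *That the documents show a raised risk after a resolved non-gastrointestinal bleed.* They do not. Epistaxis is the non-gastrointestinal bleed they list; its grade is not given, and the very common rates come from combinations with chemotherapy. The any-site rule in 3.1.2 concerns where the tumor arose, not where bleeding occurs.
- *That gastrointestinal perforation or fistula must also be named at entry.* A reader might infer this from 6.3.8: "Ramucirumab should be discontinued in the event of a GI perforation or fistula formation". But 3.2.2, 3.2.11 and 3.2.16 already give partial cover, and the documents offer no basis for choosing a look-back period.

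**Conclusion.** The point holds as a cheap improvement for patient safety. Followed as written, the specific criteria admit a patient with a recent, resolved Grade 3-4 non-gastrointestinal bleed who meets 3.1.8; only a discretionary reading of 3.2.16 would exclude that patient. The exceptions are an intracranial bleed read as a cerebrovascular accident (3.2.7, 6 months) and a bleed treated by major surgery (3.2.2, 28 days).

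Confidence is high that the text leaves this gap. There is no basis in the documents for saying how often it will matter, and the answer may be never among 43 patients. The accrual effect of 0 to 1 month rests on the assumed 0 to 2 patients and on the planned rate being met. The null and alternative medians, alpha, power and PFS analysis are unaffected.

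**What to change.** Delete the word gastrointestinal from 3.2.5, so that the criterion covers any Grade 3-4 bleeding in the 3 months before enrollment, and make the same change on the eligibility checklist. Grade and look-back stay as they are.

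The cost is one word, one checklist line, and possibly a few otherwise eligible patients excluded, or delayed until the 3 months have passed. If the restriction to the gastrointestinal tract is deliberate, one sentence giving the reason would close the point instead.
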